### **5.5 Removal of Subjects from Trial**

Subjects must be removed from the trial if:

1. Informed consent is withdrawn; or
2. The investigator or the sponsor believes it is in the best interest of the subject to be removed from the trial.

Subjects may be withdrawn from the trial if a SAE occurs. The date and reason for discontinuation should be noted on the eCRF. Subjects who discontinue prematurely should be seen for a final evaluation.

### **5.6 Premature Termination of Trial/Closure of Center**

The sponsor may discontinue the trial at any time. Reasons for discontinuation of the trial may include, but are not limited to, new information on safety or efficacy, requests from regulatory authorities, or changes in business priorities. Additional reasons for center closure may include, but are not limited to, excessive protocol violations, inadequate regard for subject safety, failure to follow recommended procedures (e.g., documentation), failure or inability to accommodate Avid/Contract Research Organization (CRO) monitors or to provide required access to data and source documents, staff turnover, inadequate staffing, and inadequate enrollment. Except in cases affecting subject safety, the investigator may complete final study evaluations for ongoing subjects. In all cases of center, or study termination, appropriate steps will be taken to ensure the safety of study subjects.

## **6. WARNINGS/PRECAUTIONS**

The most up-to-date and complete information regarding the use of flortaucipir ( $^{18}\text{F}$ ) injection can be found in the investigator's brochure.

In brief, flortaucipir ( $^{18}\text{F}$ ) injection is an experimental imaging agent that will be used at relatively low (tracer) doses. Because flortaucipir ( $^{18}\text{F}$ ) injection is under clinical investigation, it is recommended that subjects receiving flortaucipir ( $^{18}\text{F}$ ) injection be followed closely by means of adverse event reporting.

## 7. PROCEDURES AND METHODS

### 7.1 Assessment Periods (See Section 11.2, Trial Flow Chart)

The study will consist of the following sequence of activities:

#### *7.1.1 Screening Visit:*

Subjects currently enrolled in the BIOCARD study protocol will be contacted to participate. Screening assessments may take place over several days, within 90 days of the flortaucipir ( $^{18}\text{F}$ ) PET scan, and will include:

- Informed Consent will take place before any AV-1451-A20 study procedures;
- Demographics (birth year, gender, race, ethnicity, education, alcohol, drug use and smoking);
- Medical history and concomitant medications;
- For women of childbearing potential, a negative serum pregnancy test must be obtained at the screening visit.
- A physician will see the subject during the screening assessments.
- An ECG will be performed to assess the participant's cardiac status. If an ECG was performed within the last 12 months of the flortaucipir ( $^{18}\text{F}$ ) PET Imaging Visit and is available for review, the ECG does not need to be repeated.

#### *7.1.2 Imaging Visit(s)*

##### Flortaucipir ( $^{18}\text{F}$ ) PET Imaging Visit

- A physician or a licensed/credentialed medical professional (i.e., a PET technologist, imaging center nurse or a regional equivalent) designated by the site principal investigator must assess or evaluate the subject prior to administration of flortaucipir ( $^{18}\text{F}$ ) injection to determine if they are still suitable to undergo the scan. If a designee performs this activity, a physician must be available to provide medical consultation;
- For women of childbearing potential, a negative urine pregnancy test must be obtained on the day of flortaucipir ( $^{18}\text{F}$ ) dose administration;
- Subjects will receive a single IV bolus injection target dose of 370 MBq (10 mCi) of flortaucipir ( $^{18}\text{F}$ ) injection followed by a saline flush.
- At approximately 75 minutes following injection, a continuous 30-minute brain scan will begin;
- The injection site will be observed for excessive inflammation or damage to the surrounding tissue where the dose was injected;
- Adverse events will be continuously monitored during the flortaucipir ( $^{18}\text{F}$ ) PET imaging visit. Subjects who experience an adverse event will

not be discharged from the imaging center until the event has resolved or stabilized;

- A physician or a licensed/credentialed medical professional (i.e., a PET technologist, imaging center nurse or a regional equivalent) designated by the site principal investigator must assess or evaluate the subject prior to discharge from the imaging center to evaluate the subject's readiness for discharge. If a designee performs this activity, a physician must be available to provide medical consultation; and
- A follow-up phone call to the subject, or informant where applicable, will be conducted within 2 or 3 business days of the imaging day, but not before 48 hours post-injection, to confirm subject well-being and to collect information about any new adverse events. If both of these days are not business days, the follow-up phone call can occur the following business day.

## **7.2 Observations and Measurements**

### Informed Consent

Potential subjects will be allowed to read a written informed consent form. The principal investigator, or designee, will explain all study procedures, risks, and alternative therapies to the subject. The subject will have an opportunity to have all questions answered. The appropriate parties will then sign and date the informed consent form, indicating willingness to participate in the study (see Section 7.5). A copy of the signed informed consent will be given to the subject.

All informed consent forms must be approved by Avid or designee, and by the appropriate Institutional Review Board (IRB) prior to use.

### Medical History

The investigator or designee will obtain an updated history at the screening visit.

- Relevant demographic information
- Review of body systems
- Social history
- Medical and surgical history, including medical care for head trauma
- Concurrent medications

Whenever possible, the medical history will be confirmed by medical records.

### Electrocardiogram (ECG)

A resting 12-lead electrocardiogram will be recorded as part of the screening visit, unless an ECG was performed within twelve months of the flortaucipir (F) PET Imaging Visit and is available for review.

### Physician Visit

A physician must see the subject during the screening visit. A physician or a licensed/credentialed medical professional (i.e., a PET technologist, imaging

center nurse or a regional equivalent) designated by the site principal investigator must assess or evaluate the subject prior to administration of flortaucipir ( $^{18}\text{F}$ ) injection and prior to discharge from the imaging center. If a designee performs this activity, a physician must be available to provide medical consultation. At discharge, the physician or licensed/credentialed medical professional should review all safety data and briefly examine/query the subject regarding potential adverse events or other treatment issues.

### Pregnancy Testing

- Serum beta hCG, qualitative: performed at screening for females of childbearing potential (defined as pre-menopausal, less than 2 years post-menopausal or not surgically sterile). A serum pregnancy test may also be obtained prior to injection at the imaging visit if required by the local site.
- Urine beta hCG: performed at the flortaucipir ( $^{18}\text{F}$ ) imaging visit prior to injection for females of childbearing potential (defined as pre-menopausal, less than 2 years post-menopausal or not surgically sterile).

### **7.3 Protocol for Image Collection**

The sponsor will prepare and distribute imaging manuals for flortaucipir ( $^{18}\text{F}$ ) image acquisition parameters and transmission procedures prior to site initiation.

### **7.4 Good Clinical Practice and Monitoring**

All clinical studies performed under the direction of Avid/CRO will be conducted in accordance with applicable regulatory requirements and International Conference on Harmonization (ICH) Good Clinical Practice (GCP) and Avid/CRO Standard Operating Procedures (SOP).

This includes:

1. IRB approval: An investigation will be initiated at a study site only after the IRB for that study site has given their written approval of the protocol and informed consent;
2. Informed Consent: Study procedures will not be initiated until the subject signs the informed consent form;
3. Recording and monitoring of adverse events as outlined in Section 7.7.3 including the notification of study site clinical investigators, local IRBs and the FDA regarding serious adverse event;
4. Avid RP's obligation to monitor the participating center on a regular basis; and
5. The termination of a center or the trial if conditions apply, as outlined in Section 5.6.

## 7.5 Informed Consent and Subject Information

Potential subjects will be allowed to read a written informed consent form. The principal investigator or designee will explain all study procedures, risks, and alternative therapies. The subject will have an opportunity to have all questions answered by a physician. The subject will then sign and date the informed consent form, indicating willingness to participate in the study.

If the subject is not capable of giving consent, consent may be given by a legally authorized representative. However, it is expected that all subjects entering this study should at least have the capacity to understand that they are engaging in a research study and should affirm that they do not object to participating, by signing on the Subject Assent line of the consent form. If the legal guardian is also the informant, the guardian must still sign the informant line of the form, indicating their own willingness to participate as an informant.

All informed consent forms must be approved by Avid or designee, and by the appropriate Institutional Review Board (IRB). No study related procedures shall be performed prior to completion of the informed consent process, and signing of the consent form. A copy of the signed informed consent should be given to the patient for their records.

## 7.6 Documentation

Flortaucipir (F) PET scans will be saved in an appropriate electronic format as specified in the imaging manuals. A copy of all scans, including the MRI scans conducted per BIOCARD study protocol, will be saved at the site/imaging center and a copy of each will be forwarded to the sponsor described in the imaging manuals. All other data required by the protocol will be recorded in the eCRFs. All data in the eCRFs will be substantiated by “source documents,” which consist of the subject’s medical files, laboratory result sheets, ECG tracings, etc. All source documentation must be available to Avid, and its designees. Completed source documents and eCRFs may need to be made available and complete for an audit by the FDA, other international regulatory authorities, or Avid at any time. The eCRFs and all other records must be filed in accordance with applicable laws and regulations (see Section 10.6).

## 7.7 Adverse Events (AE)

Avid’s standards for recording and reporting adverse events (AEs) are to be followed regardless of applicable regulatory requirements that may be less stringent. All AEs must be fully recorded on the adverse event eCRFs. Investigators will be instructed to report to Avid, or its designee, their assessment of the potential relatedness of each AE to study drug or protocol procedure via electronic data entry. If a patient’s treatment is discontinued as a result of an AE, study site personnel must clearly report to Avid, or its designee, via electronic

data entry the circumstances and data leading to any such discontinuation of treatment. In cases where the investigator notices an unanticipated benefit to the patient, study site personnel should report “unexpected benefit” with the actual event term to Avid, or its designee (for example, the complete actual term would be “unexpected benefit- sleeping longer”).

Signs and symptoms of each AE should be described in detail (e.g., start and stop dates/time, severity/intensity, relationship to study drug, action taken, and event resolution). Additionally, any clinically significant findings from study procedures including those that result in a diagnosis should be reported as an AE to Avid, or its designee.

### ***7.7.1 Adverse Event Monitoring***

Each patient must be carefully monitored for adverse events. This includes clinical laboratory test variables. An assessment must be made of the severity/intensity and relationship to the administration of the study drug.

### ***7.7.2 Adverse Event Definitions***

#### Adverse Events

An adverse event is any undesirable experience occurring to a subject during a clinical trial, whether or not considered related to the study drug.

For reporting purposes, Avid will distinguish among pre-existing conditions, trial-emergent adverse events and treatment-emergent adverse events.

Pre-existing conditions (i.e., undesirable experiences, signs or symptoms that begin prior to the Screening Visit) will be recorded on the medical history eCRF pages. During the study, site personnel will record any change in the condition(s) and occurrence and nature of any AEs. Signs and symptoms that are believed to be due to the pre-existing condition(s) (started prior to dose of study medication) do not have to be recorded in the AEs section of the eCRF, unless there is an increase in frequency and severity.

Trial-emergent adverse events are undesirable experiences, signs or symptoms that begin, or worsen in intensity or frequency, after the informed consent, and prior to administration of the study drug at the imaging visit.

Treatment-emergent adverse events are any untoward medical occurrence associated with the use of a drug in humans, whether or not considered drug related. For the purposes of this study, untoward medical occurrences will be considered associated with the use of flortaucipir ( $^{18}\text{F}$ ), and thus be reported as adverse events, if they occur within 48 hours after flortaucipir ( $^{18}\text{F}$ ) administration.

The end of study, for the purpose of adverse event reporting, is defined as 48 hours after the last administration of flortaucipir ( $^{18}\text{F}$ ).

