8.3.2 Medical and Surgical History

Medical and surgical histories were coded using MedDRA version 19.1, and will be presented in a listing for the safety population.

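### The adverse-event recording exemption in Protocol 7.7.2 lifts only when frequency and severity both rise, so a one-way worsening after injection may be left out of the safety data

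*Protocol*

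**What the plan says.** All the main wording is in Protocol 7.7.2, under Adverse Events.

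- The general definition is broad: "An adverse event is any undesirable experience occurring to a subject during a clinical trial, whether or not considered related to the study drug".
- Pre-existing conditions are "undesirable experiences, signs or symptoms that begin prior to the Screening Visit", and they go on the medical history pages of the eCRF.
- A duty to record follows: "During the study, site personnel will record any change in the condition(s) and occurrence and nature of any AEs". No eCRF page is named for these changes.
- The exemption comes next. It covers "Signs and symptoms that are believed to be due to the pre-existing condition(s) (started prior to dose of study medication") and says that these "do not have to be recorded in the AEs section of the eCRF, unless there is an increase in frequency and severity".
- Trial-emergent events are those that "begin, or worsen in intensity or frequency, after the informed consent, and prior to administration of the study drug at the imaging visit".
- Treatment-emergent events are untoward occurrences within 48 hours after injection. The protocol gives no criterion for worsening here, and SAP 6.6.2 repeats the 48-hour rule, also without one.

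SAP 8.5.2 to 8.5.8 build the TEAE, severity, relationship, seriousness, discontinuation and death summaries, and the AE listing, from recorded adverse events. Under SAP 8.3.2, medical and surgical history "will be presented in a listing for the safety population".

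**The concern.** One section uses two thresholds for the same kind of change. The trial-emergent definition accepts a rise in intensity or in frequency. The exemption asks for both before entry in the AE section becomes mandatory. After injection, the period that matters for tracer safety, the exemption is the only text that says how worsening of an old complaint is to be handled.

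An event left out at the site cannot be recovered by any definition in the SAP, because the SAP's safety tables start from what was entered. Expanding the safety database is the study's only secondary objective. Aggravation of an existing complaint after the injection and scan is one of the things such a database should be able to show.

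**Working it through.** The documents give no figure to reproduce, so the check is a reading of the rules, followed by one piece of arithmetic.

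**Step 1: the four possible changes after injection**, for a symptom that the site attributes to a pre-existing condition.

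| Change after injection | AE entry under the exemption as written (*and*) | AE entry if the exemption used *or* |
|---|---|---|
| Neither rises | Not required | Not required |
| Frequency only | Not required | Required |
| Severity only | Not required | Required |
| Both rise | Required | Required |

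The conjunction changes the outcome in the two middle rows. For example, a chronic headache that goes from mild to severe with the same number of episodes falls in the third row, provided the site attributes it to the old condition.

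**Step 2: before injection.** The exemption is not limited to the post-injection period. A one-way worsening between consent and injection is therefore a trial-emergent event by definition and exempt from AE entry by the other sentence. The two collide directly.

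**Step 3: does other text close the gap?**

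- Protocol 7.7, 7.7.3 and 10.7 require all adverse events to be recorded. These are general duties. The exemption is the specific instruction for this case, and a site could follow it in good faith.
- The duty to record any change in a pre-existing condition has no threshold but names no page. The flow chart in Protocol 11.2 schedules medical history at screening only.
- The follow-up call (Protocol 5.1, 7.1.2 and 11.2) asks about new adverse events, which does not clearly prompt for worsening of an old one.
- Protocol 7.7.4 collects serious events until 48 hours after dosing, whatever the investigator's view of causation. That covers serious worsening only.

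**Step 4: classification once entered.** Changing the conjunction is not enough. Neither TEAE definition says whether a condition that began before injection and worsened after it is treatment-emergent. SAP Appendix I, for missing or partial onset dates, decides on onset and stop dates alone and does not consider worsening.

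**Step 5: the start-date wording.** Pre-existing means begun before the Screening Visit, whereas the parenthesis in the exemption refers to a start before dosing. Screening may precede the scan by up to 90 days, or longer with sponsor approval. A complaint that starts in that gap is trial-emergent under one sentence and arguably exempt under the other.

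**Step 6: weight of one subject.** SAP 4.4 gives 23 subjects dosed with an accompanying visual read or quantification. If that is the safety population, one subject whose only event is omitted changes the TEAE percentage by 1/23 = 0.0435, or 4.3 percentage points. If other subjects were dosed without a read, the denominator is larger and the weight slightly smaller.

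**The case against.** The strongest reply is that this is loose drafting and not a loss of data. Several parts of that reply stand.

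- A reader might infer that one-way worsening is never recorded as an adverse event. The text does not say so. It waives an obligation without prohibiting entry, and the general duties and the 48-hour rule point towards recording.
- A reader might infer that a symptom must rise in both respects before it counts as an adverse event. That confuses a recording exemption with the definition, which contains no such test.
- The exemption reaches only symptoms that the site attributes to the old condition. A headache that becomes severe some hours after injection is exempt only if the site makes that judgement.
- Serious events are collected separately, and clinically relevant laboratory, vital-sign and ECG abnormalities go on the AE pages under Protocol 7.7.3.
- The parenthesis can be read as a further limit on conditions already defined as pre-existing, so the screening-versus-dosing point is an ambiguity and not a proven contradiction.
- Rewording the protocol cannot change what was captured for subjects already dosed.

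What does not stand is the claim that the general duties settle the matter. A specific exemption beside a general rule leaves the site to choose, and different staff may choose differently. The sentence on recording any change does not say where, so it does not ensure that the change reaches the AE data.

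**Conclusion.** The inconsistency is real and bears on the secondary safety objective. Following the exemption as written, a site may leave out of the AE section a post-injection worsening in frequency alone or severity alone that it attributes to a pre-existing condition. Capture can then be inconsistent, and TEAE incidence may be understated.

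The size is unknown. It is tempting to say that the rule loses most aggravations, since it exempts two of the three ways of worsening. That counts categories, not events. The documents give no rate of aggravation within 48 hours of a single tracer dose, no information on how often frequency and severity rise together, and no account of how the site applied the rule. The number of omitted events could be zero. The only firm figure is the weight of one subject, 4.3 points, and it assumes a safety population of 23.

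**What to change.** 1. In Protocol 7.7.2, make a rise in either frequency or severity lift the exemption, to match the trial-emergent definition. Carry this into any eCRF completion instructions.
2. Align the parenthesis in the exemption with the Screening Visit definition of a pre-existing condition.
3. State the same worsening criterion in the TEAE definitions of Protocol 7.7.2 and SAP 6.6.2, so that an aggravation after injection is classified as well as captured.
4. For the 23 subjects already dosed, review the source files (Protocol 10.6), any recorded changes in pre-existing conditions, and the follow-up contact data (SAP 8.5.10) for worsening within 48 hours of injection. Enter qualifying events as adverse events. The medical history pages alone will not do, because that assessment is scheduled only at screening.
5. Report the recording rule that was in force alongside the safety results, so that readers can judge the completeness of the AE counts.

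The cost is a few wording changes and a small data review. The reported AE count may rise slightly. The review can find only what was noted at the time, so step 5 is needed even if it finds nothing.

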6.6.2 Adverse Events

An AE is any undesirable experience occurring to a subject during a clinical trial, whether or not considered related to the study drug. AEs are classed by severity and seriousness.

Treatment-emergent adverse events (TEAE) are any untoward medical occurrences associated with the use of a drug in humans, whether or not considered drug related. For the purposes of this study, untoward medical occurrences will be considered associated with the use of flortaucipir, and thus be reported as TEAEs if they occur within 48 hours after administration of the PET tracer. The end of study for the purpose of AE reporting is defined as 48 hours after the administration of flortaucipir injection.

The investigator's verbatim term of both serious and non-AEs will be mapped to system organ class (SOC) and preferred terms (PT) using the Medical Dictionary for Regulatory Activities (MedDRA) Version 19.1.

Severity is classified as mild/moderate/severe (increasing severity). If a subject reports a TEAE more than once within that SOC/PT, the TEAE with the worst case severity will be used in the corresponding severity summaries.

Serious AEs (SAEs) are events that result in one of the following outcomes or constitute one of the following events:

- Death

- Initial or prolonged hospitalization (other than that required by protocol; “social hospitalization” or any hospitalization for non-medical reasons does not constitute an SAE)
- A life-threatening experience (that is, immediate risk of dying)
- Persistent or significant disability/incapacity
- Congenital anomaly/birth defect
- Considered significant by the investigator for any other reason

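### Protocol 7.7.2 lets sites leave worsening of a pre-existing condition off the AE page unless frequency and severity both rise; this conflicts with the section's own AE definitions, so AE and TEAE counts may be too low

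*Protocol*

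**What the plan says.** Protocol 7.7.2 separates pre-existing conditions, trial-emergent AEs and treatment-emergent AEs (TEAEs).

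- **Pre-existing conditions** are those beginning before the Screening Visit, and they go on the medical history pages. Site staff are to note changes in them during the study, but no eCRF page is named for this. The next sentence excuses sites from an AE-section entry for any sign or symptom attributed to such a condition, "unless there is an increase in frequency and severity". A parenthesis in that sentence dates the symptoms as "started prior to dose of study medication".
- **Trial-emergent AEs** are experiences that "begin, or worsen in intensity or frequency, after the informed consent, and prior to administration of the study drug at the imaging visit".
- **TEAEs** are untoward occurrences, drug-related or not, which count as associated with the tracer "and thus be reported as adverse events, if they occur within 48 hours after flortaucipir" administration. SAP 6.6.2 repeats this: they are TEAEs "if they occur within 48 hours after administration of the PET tracer".

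Protocol 7.7 and 7.7.3 require all AEs to be fully recorded on the AE eCRF, and Protocol 10.7 likewise wants every AE documented on the eCRF. SAP 8.5.2 tabulates TEAEs and presents all AEs in a listing. Expanding the safety database is the only secondary objective (Protocol 2, SAP 3).

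**The concern.** The recording rule and the definitions use different tests. A worsening on one dimension before dosing is an AE by definition and must be recorded under 7.7 and 7.7.3, yet 7.7.2 excuses it from the AE page. The exemption does not end at dosing. Because it is tied to symptoms that started before the dose, it also governs how those symptoms are recorded after injection, the period that feeds the TEAE tables.

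Two sites, or two coordinators at one site, could follow the protocol faithfully and record the same event differently. An event left off the AE page cannot appear in the AE listing or the TEAE tables, and those outputs carry the adverse-event part of the safety objective.

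**Working it through.** The plan states no figure on this point, so the check is a comparison of the rules, followed by the direction and scale of the effect.

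**Step 1. Apply each rule to the same cases.** Take a condition known before screening, with symptoms the investigator attributes to it.

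| Worsening | When | AE under the 7.7.2 definitions? | AE-page entry required by the 7.7.2 exemption sentence? |
|---|---|---|---|
| Severity only | Consent to dose | Yes, trial-emergent | No |
| Frequency only | Consent to dose | Yes, trial-emergent | No |
| Both | Consent to dose | Yes, trial-emergent | Yes |
| Severity only | Within 48 h after injection | Yes, if worsening is an untoward occurrence | No |
| Frequency only | Within 48 h after injection | Yes, on the same reading | No |
| Both | Within 48 h after injection | Yes, on the same reading | Yes |

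Four of the six rows conflict. A symptom that is constantly present cannot become more frequent, so read literally it can never meet the joint test, however severe it becomes. Elsewhere in 7.7.2, the definition of an unexpected AE also joins severity and frequency with *or*, so the *and* in the exemption stands alone.

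**Step 2. Direction.** Let f, s and b be the numbers of worsenings in frequency only, in severity only, and in both.

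- Events meeting an *or* test: f + s + b.
- Events whose recording is required under the *and* test: b.
- Required share: b / (f + s + b).

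Events meeting *and* are a subset of those meeting *or*, so the rule can only lower the count or leave it unchanged. The documents give none of f, s or b, and the share can lie anywhere from 0% (b = 0) to 100% (f = s = 0). If the three types were equally common, which is an assumption made only to illustrate, it would be 1/3. Sites may record more than is required, so the shortfall is at most (f + s) / (f + s + b).

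**Step 3. Does the SAP repair it?** I find no provision that does.

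- SAP 6.6.2 repeats the 48-hour rule without mentioning worsening.
- SAP 8.3.2 only lists medical history, so a change noted there reaches no AE table.
- Appendix I classifies events with missing or partial dates by whether onset could fall within 48 hours after injection. A worsened condition entered with a partial original onset date that is clearly before injection comes out as not TEAE.
- The flow charts (Protocol 11.2, SAP 6.1) schedule medical history at screening only.

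**Step 4. Scale of one event.** SAP 4.4 reports 23 subjects dosed who had a visual read or quantification. If 23 is also the safety denominator, one subject whose only TEAE is unrecorded changes incidence by 1/23 = 0.043, or 4.3 percentage points. The safety population in SAP 8.1.2 is everyone injected; if that is larger, the figure is smaller.

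**The case against.** The strongest reply is that this is a drafting mismatch with little practical effect. Several parts of that reply stand.

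- The exemption is permissive. A reader might infer that one-dimensional worsening is never captured, but the text does not forbid recording it and asks staff to note changes.
- It covers only symptoms believed to be due to the pre-existing condition. A worsening the investigator attributes to something else is not exempt.
- The *or* wording belongs to the period before dosing, and trial-emergent AEs are listed, not tabulated. The effect on TEAE tables comes from a second conflict, between the exemption and the broad 48-hour definition.
- A reader might infer that the TEAE definition excludes worsening because it does not mention it. The definition is wide enough to include a symptom that becomes severe after injection.
- A reader might infer two cut-offs for pre-existing conditions, with symptoms arising between consent and dose both trial-emergent and exempt. The parenthesis may simply describe the symptoms and leave the Screening Visit cut-off intact. The text is ambiguous, and that is all it shows.
- Serious events are collected for 48 hours after dosing whatever the opinion on causation (Protocol 7.7.4), so any loss should be mainly of non-serious events.

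None of this removes the conflict. The instruction to note changes names no eCRF page and is followed at once by the exemption from the AE section, and the SAP does not say how a worsened pre-existing condition is classified.

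**Conclusion.** The concern holds as a conflict between the recording rule and the AE definitions in Protocol 7.7.2, left unresolved by the SAP. Followed as written, the rule lets worsening in severity alone or frequency alone stay out of the AE data, including within 48 hours after injection. AE and TEAE counts may be too low.

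The direction is certain relative to an *or* rule; the size is not known. It depends on how often attributed symptoms worsened on one dimension and how often sites recorded them anyway. It is tempting to state a percentage lost by assuming rates and independence of the two dimensions, or to say that the counts are biased. The documents supply no rates, and severity and frequency of one condition may well move together, so neither statement is supported. The 4.3 points per subject is a scale, conditional on 23 being the denominator.

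The consequence is modest: a single tracer dose, a 48-hour window and a descriptive secondary objective. It is still worth correcting, because the rule is operative and the correction is cheap.

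**What to change.** 1. In Protocol 7.7.2, change the exemption to frequency *or* severity, so that recording follows the definition.
2. Clarify whether the parenthesis about symptoms starting before the dose alters the Screening Visit cut-off for pre-existing conditions.
3. In SAP 6.6.2 and Appendix I, state that a pre-existing condition whose worsening begins within 48 hours after injection is a TEAE, classified by the onset of the worsening.
4. SAP 4.4 describes dosing in the past tense, so new protocol wording cannot change what was collected from those subjects. Review any recorded changes in pre-existing conditions within 48 hours of injection, where such records exist. Because medical history is scheduled only at screening, they may not. In that case, state in the CSR that one-dimensional worsening may be under-recorded.

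The cost is a few words in each document, plus a limited data review or one sentence in the CSR. The downside is that AE counts may rise slightly.
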